3.2.4. Duration of Event

Where the duration of an event is to be calculated, it will be derived as:

Duration (days) = (Event stop/end date – Event start date) + 1.

Duration (months) = Duration (days) / 30.4375

3.2.5. Retest and Unscheduled Visits

Unscheduled measurements and retests will not be included in by-visit summaries but will contribute to incidence of significant abnormality tables, where applicable.

In the case of a retest (same visit number assigned), the last available measurement for that visit will be used for by-visit summaries.

3.2.6. Study Treatment Periods

Period	Definition
Pre-treatment Period	Date of Screening through one day prior Date of first dose
Double-blind	Date of first dose through one day after Date of last dose

Treatment Period	OR
	Date of first dose through one day prior first dose during open-label treatment
	period
Open label Long-	Date of first dose during open-label LTE period (Part B) to Date of last dose
term Extension	during open-label LTE period (Part B or C) plus one
Periods	OR
	Date of first dose during open-label LTE period (Part B) through one after Date of
	last dose during open-label continued-LTE period (Part C)

3.2.7. Coding Dictionary

Where applicable, safety data will be coded using the following coding dictionaries:

Dictionary	Version
Medical Dictionary for Regulatory Activities (MedDRA)	25 or higher
World Health Organization Drug Dictionary (WHODrug Global)	WHODrug-Global-B3 Sep 2021 or later

3.2.8. ALS Functional Rating Scale - Revised (ALSFRS-R) score

The ALSFRS-R is a quickly administered (5-minute) ordinal rating scale that assesses the subjects' capability and independence in 12 functional activities across 4 subdomains of bodily function (bulbar, gross motor, fine motor, and respiratory) relevant in ALS. Each activity is recorded to the closest approximation from a list of 5 choices, scored 0 (total loss of function) to 4 (no loss of function), with the total score ranging from 0 to 48 and higher scores indicating less functional impairment (Cedarbaum 1999).

The score change from baseline will be calculated as the post baseline score minus the baseline score, so that a positive score for change from baseline would indicate improvement in function relative to baseline, while a negative score indicates worsened disease relative to baseline.

Subdomains	Items
Bulbar	Speech, Salivation and Swallowing
Fine Motor	Handwriting, Cutting Food/Handling Utensils and Dressing Hygiene
Gross Motor	Turning in Bed, Walking and Climbing Stairs
Respiratory	Dyspnea, Orthopnea and Respiratory Insufficiency

3.2.9. Pulmonary Function Tests

Pulmonary function tests are used to assess respiratory function. Pulmonary function tests (PFTs) will assess SVC and SNIP. Forced vital capacity, vital capacity, forced expiratory volume, and maximum inspiratory pressure will not be measured. Oxygen saturation (SpO2), respiratory rate, and heart rate will be assessed in both upright and supine positions. The SNIP test will assess nasal pressure in each unilaterally occluded nostril during a maximal sniff to assess inspiratory muscle strength.

3.2.10. Modified Norris Scale

Modified Norris scale is used to assess the motor/limb and bulbar function. The Modified Norris Scale is a rating scale for ALS that consists of 2 parts: the Limb Norris Scale and the Norris Bulbar Scale. The Limb Norris Scale has 21 items to evaluate extremity function, and the Norris Bulbar Scale has 13 items to evaluate bulbar function. Each item is rated in 4 ordinal categories. The total score is calculated by summing all the scales (Norris 1974).

3.2.11. ALS Cognitive Behavioral Screen

The ALS CBS is a brief measure of cognition and behavior in patients with ALS. The ALS CBS is composed of 2 sections: cognitive and behavioral. The cognitive section includes commonly used elements of standard testing batteries, consisting of 8 tasks that assess attention, concentration, tracking/monitoring, and initiation and retrieval. Each subtest score ranges from 0–5 and the total score ranges from 0–20. The behavioral section is composed of questions sensitive to organic brain changes. It consists of fifteen 3-point Likert items (total score ranges from 0–45) questioning caregivers on patients' behavioral changes (3 = "no change"; 0 = "large change") and 4 "yes/no" questions on anxiety and depression.

3.2.12. ALSAQ-40 Assessment

The ALSAQ-40 is a disease-specific measure of health-related quality of life for ALS (Jenkinson 1999). It is specifically used to measure the subjective well-being of patients with ALS and provides scores for 5 scales: physical mobility (10 items: 1-10), activities of daily living and independence (10 items: 11-20), eating and drinking (3 items: 21-23), communication (7 items: 24-30) and emotional reactions (10 items: 31-40). If one of the question items of ALSAQ-40 is missing, the total score will be considered as a missing value. However, it may be included in the summary of the specific scales. Lower total scores for the ALSAQ-40 indicate better quality of life, with higher scores indicating poorer quality of life. Analyses will be performed on the total score.

3.2.13. EuroQol EQ-5D-5L

The EQ-5D-5L is a patient reported outcome measure (PROM) that determines a subject's health-related quality of life (www.euroqol.org). EQ-5D-5L consists of 2 components: The health state descriptive system and the visual analogue scale (EQ-VAS). The health state descriptive system is a 5 Dimension (5-D) questionnaire covering 5 health related aspects: Mobility, self-care, usual activities, pain/discomfort and anxiety/depression. For each Dimension, the subject responds by selecting one of 5-levels (5L): 1=No problems; 2=Slight Problems; 3=Moderate Problems; 4=Severe Problems and 5=Extreme Problems.

The visual analogue scale (EQ-VAS) is a 20 cm vertical graduated visual analogue scale with numbers ranging from 0 (=worst imaginable health) to 100 (=best imaginable health). Subjects rate their overall health by placing an X mark on the scale to indicate their perceived overall health.

3.2.14. Survival

The survival endpoint is defined as the time from the randomization date to the date of death from any cause.

3.3. Interim Analysis

No formal interim analyses are planned for this study. However, At the time of the database lock of the double-blind treatment period (Part A) selected data from the open-label long term extension periods (combined Parts B and C) will be descriptively summarized and included in the interim clinical study report. This (select data) will include:

- All available safety endpoints described in Section 6
- All available survival data
- All available ALSFRS-R data
- All available ALSAQ-40 data

3.4. Changes to Protocol Specified Analysis

Safety data for Parts B and C will be combined, as the transition from Part B to Part C does not represent a clinically significant timepoint.

4. SUBJECTS DATA

4.1. Subject Disposition

Subject disposition data will be summarized. A summary table of subject disposition will be produced reflecting:

4.1.1. Subject Disposition – Part B

- Subjects completed in Part A
- Subjects enrolled (or consented) in part B
- Safety analysis set for Part B (Subjects received treatment in Part B)
- Subjects completed in Part B
- Subjects who early terminate the study treatment during part B and reasons for early termination
- Subjects who early terminate the study in Part B and reasons for early termination

4.1.2. Subject Disposition – Part C

- Subjects completed in Part A
- Subjects completed in Part B
- Subjects enrolled (or consented) in part C
- Subjects dosed in Part C
- Subjects completed in Part C
- Subjects who early terminate the study treatment during part C and reasons for early termination
- Subjects who early terminate the study in Part C and reasons for early termination

For the enrolled population in the LTE parts, the number and percentage of participants in each analysis population will be presented.

4.2. Demographics and Baseline Characteristics

Subjects' demographics and baseline characteristics will be summarized overall and by treatment group for subjects in the safety analysis sets for Part B and C.

Continuous variables (e.g., age and weight) will be summarized using descriptive statistics (n, mean, standard deviation, median, minimum, and maximum). Qualitative variables (e.g., sex, race, and ethnicity) will be summarized with counts and percentages.

The demographic parameters will include age category (<65 and ≥65 years), gender, race, and ethnicity. Age will also be summarized as a continuous variable. The baseline parameters include, height, body weight, BMI, ALSFRS-R score, amount of change in ALSFRS-R score during the screening period (<1, 1-2, 3-4, or >4 points total loss) use of standard of care (SoC) medications for ALS at baseline and disease characteristics at screening.

By-subject listings of demographic and other baseline characteristics will be provided for all randomized subjects. In this listing flag variables will be used to identify subjects in various analysis sets.

4.3. Disease Characteristics

Subjects' disease characteristics will be summarized for subjects in the Long-Term Extension Safety Analysis. By-subject listings of disease characteristics will also be provided. Duration of symptoms (months) and months since diagnosis will be summarized using descriptive statistics (n, mean, standard deviation, median, minimum, and maximum). The following disease characteristics will be summarized with counts and percentages (n (%)):

- Site of symptom onset
- Family history
- El Escorial criteria at screening
- Pre-ALS impairment
- Months since ALS symptom onset
- Months since diagnosis
- Site of onset
- Diagnosis delay
- Derived King's Clinical Stage (Balendra 2014 also see Appendix 5)
- TRICALS Risk Profile

The TRICALS risk profile (van Eijk 2021) is based on the European-Network-to-Cure-ALS survival prediction model, a cross-validated model to predict the composite endpoint death or respiratory insufficiency based on data of 11,475 subjects with ALS (Westeneng 2018). The TRICALS Risk Profile is a weighted average of seven pre-randomization subject characteristics, including: Percent predicted vital capacity, age at onset in years, diagnostic delay (months from symptom onset to diagnosis), presence of frontotemporal dementia, progression rate of the ALS functional rating scale (points per month), Bulbar onset of ALS, and an El Escorial criteria of clinically definite ALS at screening. The range of possible values for this summary predictor is from approximately -12.0 to 0.0 with higher scores indicating a poorer prognosis. Section 13 (Appendix 3) provides details on its derivation.

4.4. Medical History

Medical and surgical history will be provided for subjects in the long-term extension safety set sets for Part B and C. Medical history will also be provided for all subjects who were exposed to the investigational product (PTC857).

Medical and surgical history will be coded using a central coding dictionary, the Medical Dictionary for Regulatory Activities (MedDRA) terminology.

Medical and surgical history will be defined as any significant past medical conditions that ended before screening or current medical conditions that were ongoing at Screening. Medical and surgical histories will be summarized separately by system organ class (SOC) and preferred term

(PT) overall and for each treatment group for the safety analysis set. Summaries will be sorted alphabetically by SOC, and by descending order of frequency for PTs according to the total column. Subjects with more than one of the same PTs within an SOC will be counted only once. A by-subject listing will be provided for the safety analysis set.

4.5. Prior Medications and Concomitant Medications

Prior medications are medications which started and stopped before the first dose of study drug. Any changes to prior medications (dose, regimen, etc.) during the study will be considered a new concomitant medication. In the analyses of subjects exposed to the investigational product (PTC857) prior medications will be defined as medications started and stopped before the first dose of PTC857.

Concomitant' medications/procedure are medications/procedures which started prior to or after the first dose of study drug and ended after the date of first dose of study drug or ongoing at the end of the study. If a medication or procedure cannot be classified as "prior" or "concomitant" after applying imputation rules for missing/incomplete dates, it will be classified as concomitant.

Prior and concomitant medications will be coded using the latest available version of the Anatomical Therapeutic Chemical (ATC) classification text from the World Health Organization Drug Dictionary (WHO DD) and summarized separately. The number and percentage of subjects taking a medication will be displayed by therapeutic class (ATC Level 3) and preferred name. Summaries will be sorted alphabetically by ATC-Level 3, and by descending order of frequency for preferred name according to the total column. Subjects with more than one of the same preferred names within an ATC-Level 3 will be counted only once. Prior medications and concomitant medications will be summarized for subjects in the LTE safety analysis set and for the subjects exposed to PTC857.

Prior and concomitant procedures will be coded using the Medical Dictionary for Regulatory Activities (MedDRA) terminology.

The count and percentage of subjects who have undergone various prior and concomitant procedures will be summarized by treatment received.

A by-subject listing of prior and concomitant medications will be provided for the safety analysis set.

4.6. Multiplicity

There will be no multiplicity consideration.

4.7. Missing Data

For the analysis of change from baseline in ALSFRS-R at weeks 52 and 160, missing outcome data will be assumed to be missing at random (MAR) and will be imputed implicitly using a mixed model repeated measures analysis.

4.8. Treatment Compliance

Percent compliance will be calculated as the amount of dose taken divided by the amount of dose that should have been taken multiplied by 100. The following formula will be used to calculate compliance.

Compliance (%) =
$$\frac{100 \times (2 \times treatment \ duration \ in \ days - number \ of \ missed \ doses)}{2 \times treatment \ duration \ in \ days}$$

The extent of exposure to study medication (treatment duration) in days will be calculated as the last dose date minus the first dose date + 1.

Exposure (number of days) and compliance will be summarized descriptively (number of doses taken / number of doses expected and percentage) for the LTE safety analysis set and for subjects exposed to PTC857.

4.9. Visit Windows for The Early Termination Visit and Unscheduled Visits

If a subject completely withdraws from the study prematurely, and unless consent is withdrawn, all efforts are made to collect efficacy and safety data and to complete the Early Termination Visit (ET).

Follow-up efficacy data collected at the early termination visit will be incorporated into the study visit schedule using the visit windows, defined in Table 1, Table 2 and Table 3. Similarly, follow-up efficacy data collected during unscheduled visits or make-up visits will also use the same visit windows. If a follow-up visit (ET) or unscheduled visit falls in the same visit window as a scheduled visit, then the scheduled visit data will be used. If an unscheduled visit and ET visit fall within the same window, then the visit closest to the target day will be used.

Table 1: Visit Windows for The Early Termination and Unscheduled Visits

		ALSFRS-R	
Visit	Lower Bound	Target Day	Upper Bound
Day 29	15	29	42
Day 57	43	57	70
Day 85	71	85	98
Day 113	99	113	126
Day 141	127	141	154
Day 169	155	169	182
Day 197	183	197	210
Day 225	211	225	238
Day 365	351	365	378
Day 449	435	449	462
Day 533	519	533	546
Day 617	603	617	630
Day 701	687	701	714
Day 785	771	785	798
Day 869	855	869	882
Day 953	939	953	966
Day 1037	1023	1037	1050
Day 1121	1107	1121	1134

Table 2: Visit Windows for The Early Termination and Unscheduled Visits

	SVC, Norris Scale, and plasma NfL		
Visit	Lower Bound	Target Day	Upper Bound
Day 85	64	85	106
Day 169	148	169	190
Day 253	232	253	274
Day 365	344	365	386

Table 3: Visit Windows for The Early Termination and Unscheduled Visits

		ALSAQ-40	
Visit	Lower Bound	Target Day	Upper Bound
Day 85	64	85	106
Day 169	148	169	190
Day 253	232	253	274
Day 365	344	365	386
Day 449	428	449	470
Day 533	512	533	554
Day 617	596	617	638
Day 701	680	701	722
Day 785	764	785	806
Day 869	848	869	890
Day 953	932	953	974
Day 1037	1016	1037	1058
Day 1121	1100	1121	1142

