 - Blood samples for PTC857, riluzole, edaravone, and/or sodium phenylbutyrate/taurursodiol PK will be collected from those subjects taking part in the PK Sub-Study at predose (prior to the first dose of the day) and at 1, 2, 4, 5, 6, 8, and 12 hours (±15 minutes) (prior to the second dose) post-dose on Day 1 and Day 29. Blood samples for PTC857 PK only will be collected predose (prior to the first dose of the day) and at 1 hour (±15 minutes) and 4 hours (±1 hour) post-dose on Day 85, and predose only at all subsequent visits with blood PK sampling. Subjects should be instructed not to take riluzole, edaravone, and/or sodium phenylbutyrate/taurursodiol on Day 1 or Day 29 prior to the study visit. Time of last dose of study drug and riluzole, edaravone, and/or sodium phenylbutyrate/taurursodiol prior to the study visit should be recorded.
 - Additional samples of predose (trough) CSF will be collected for PK evaluation at all lumbar puncture timepoints.
 - Additional ECG measurements will be performed at the time of the 4-hour and 8-hour post-dose PK samples (±15 minutes from PK sample blood draw).
- ² The lumbar punctures for CSF collection in the PK Sub-Study may occur within 5 days prior to or after the scheduled visit day.

Table 2: Schedule of Assessments for the Long-Term Extension Period (Part B)

| | | EOS/ Follow-Up | Early Termination | | | | | |
|--|-----------------|--------------------|----------------------|--------------------|-----------------|--------------------|------------------|----------------|
| Study Day | Day 169 (±3) | Day 183 (±3) | Day 197 (±3) | Day 225 (±3) | Day 253 (±3) | Day 365 (±5) | Day 393 (±3)ª | ET⁵ |
| | | | | | | End of Treatment c | | |
| Telephone call/in-home or in-person visit ^d | IP | PC/IH ^d | PC/IH ^d | PC/IH ^d | IP | IP | PC | IP |
| Informed consent | Xe | | | | Xf | Xg | | |
| Weight and BMI | | | | | Х | X | | Х |
| Serum/urine pregnancy test (female subjects only) ^h | | | (Monthly | / [Days 197, 225 | , 253, 281, 309 | , 337, and 365]) | X | X |
| 12-Lead ECG ⁱ | | | , , | | X | X | | Х |
| Vital signs ^j | | | Х | Х | Х | Х | | Х |
| Physical exam ^k | | | | | Х | Х | | Х |
| PK blood sample | | | | | Х | X | | Х |
| Clinical laboratory tests ^m | | Xn | Х | Х | Х | X | | Х |
| Laboratory biomarkers (blood and urine)° | | | | | Х | X | | Х |
| ALSFRS-R ^p | | | Х | Х | Х | Х | Х | Х |
| PFTs ^q | | | | | Х | X | | Х |
| ALS CBS | | | | | Х | Х | | Х |
| Modified Norris Scale | | | | | Х | X | | Х |

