| ALSAQ-40 | | | | | Х | X | | Х |
| EQ-5D-5L | | | | | Х | Х | | Х |
| C-SSRS ^r | | | X | Х | Х | Х | X | Х |
| Study drug dispensation | X | | | | Х | | | |
| Adverse events | | Χ | X | X | X | X | X | X |
| Prior/concomitant medications | | Χ | X | X | X | X | X | X |
| Mammogram ^s | X | | | | | X | | X ^t |

Abbreviations: ALS, amyotrophic lateral sclerosis; ALS CBS, ALS Cognitive Behavioral Screen; ALSAQ-40, ALS Assessment Questionnaire; ALSFRS-R, ALS Functional Rating Scale-Revised; BMI, body mass index; CAFS, Combined Assessment of Function and Survival; CSF, cerebrospinal fluid; C-SSRS, Columbia-Suicide Severity Rating Scale; ECG, electrocardiogram; EOS, end of study; EQ-5D-5L, five-level European quality of life five-dimensional questionnaire; ET early termination; ICF, Informed Consent Form; IH, in-home; IP, In-person; LTE, Long-Term Extension; PC, telephone call; PFT, pulmonary function test; PI, Principal Investigator; PK, pharmacokinetic

^a Follow-up Visit on Day 393 only for subjects who choose not to enter the Continued LTE Period (Part C).

^b For subjects who early terminate from the study and consent to continued follow-up, the investigator should attempt to gain vital status on the participant and conduct the ALSFRS-R assessment approximately every 28 days for the remaining duration of the study, in accordance with local requirements/regulations.

Day 365 will be considered the End of Treatment Visit only for those who choose not to enter the Continued LTE Period (Part C).

^d For the telephone call/in-home visit, where applicable, the ALSFRS-R, C-SSRS, adverse events, and prior/concomitant medications assessments will be conducted via a telephone call. Vital signs assessments and samples for clinical laboratory tests will be collected via a home health nurse during applicable inhome visits at the subject's home during these visits. Subjects may go to the site for an in-person visit at the discretion of the PI. Visits indicated as in-person only may be conducted remotely (ie, in-home) following discussion between the site and the medical monitor. In-person visits that are conducted remotely must include the following assessments, at minimum (if such assessments are typically included during the visit): serum/urine pregnancy test (females only), vital signs, clinical laboratory tests, ALSFRS-R, C-SSRS, adverse events, prior/concomitant medications, sparse PK blood sampling, laboratory biomarkers, and ALSAQ-40.

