5.2.1. Change from Baseline in ALSFRS-R

Change from baseline in ALSFRS-R at Weeks 52 and 160 will be evaluated by means of a mixed model repeated measures analysis using all available ALSFRS-R scores up to Week 160.

The model will include fixed categorical effects of treatment (PTC857 or placebo), use of approved background therapy for ALS at screening (Yes vs No), the amount of change in the subject's ALSFRS-R score during the Screening Period (<1, 1-2 or 3-4 points total loss), time of collection (nominal week at the visit as a categorical variable), as well as the continuous, fixed covariates of baseline ALSFRS-R, and The TRICALS risk profile. In addition, the following interaction terms will be included: Time by treatment, time by baseline ALSFRS-R, and TRICALS risk profile by time. Subject will be included as a random effect. The Restricted Maximum Likelihood (REML) estimation approach will be used with the variance-covariance structure set as unstructured (UN). Other types of covariance matrices will be explored in the case of non-convergence of the UN. Subjects with no post baseline results for the outcome variable will be excluded. This analysis will be performed for both the ITT1 and ITT2 analysis sets.

Observed and change-from-baseline values will also be summarized descriptively at each visit.

In supplementary analyses, score changes from baseline at Weeks 52 and 160 for the ALSFRS-R subdomains will be analyzed under the same estimand framework where MMRM models will be used to implicitly impute missing data. Nominal P-values for the treatment arm comparison, estimate of LSMEANS for the treatment differences (PTC857 – Placebo) at Weeks 52 and 160, and the two-sided 95% confidence intervals of the LSMEANS difference will be presented.

To determine if there is a reduction in the decline of ALSFRS-R scores in subjects randomized to placebo after starting open-label PTC857, graphical plots comparing the decline during the double-blind period and the open-label extension periods will be provided. Additionally, changes (in ALSFRS-R) from both the initial study baseline and the treatment baseline in Part B will be reported.

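### The Parts B/C SAP's ALSFRS-R window table omits the scheduled Day 253 visit, so early-termination, unscheduled and make-up scores from Days 239–266 have no nominal visit

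*SAP*

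**What the plan says.** Section 4.9 of the Parts B/C SAP places data from outside the regular visits into the schedule: "Follow-up efficacy data collected at the early termination visit will be incorporated into the study visit schedule using the visit windows". Unscheduled and make-up visits use the same windows, and a scheduled visit takes precedence within its window.

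The ALSFRS-R windows are in "Table 1: Visit Windows for The Early Termination and Unscheduled Visits". Two consecutive rows read "Day 225 211 225 238" and "Day 365 351 365 378". Table 2 (SVC, Norris Scale and plasma NfL) and Table 3 (ALSAQ-40) in the same section both contain the row "Day 253 232 253 274".

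The Part B schedule (protocol Table 2, repeated in Appendix 1 of this SAP) has the visit columns "Day 197 (±3) | Day 225 (±3) | Day 253 (±3"), and the ALSFRS-R row is marked at each of these three visits.

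Section 5.2.1 analyses change from baseline at Weeks 52 and 160 with a mixed model for repeated measures (MMRM) "using all available ALSFRS-R scores up to Week 160". Time enters as a categorical factor based on the nominal week.

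**The concern.** A score can enter a model with categorical nominal time only if it belongs to a nominal visit. For early-termination, unscheduled and make-up scores, Table 1 is what assigns the visit. Without a Day 253 row, a score taken close to that visit but outside it has no level of the time factor. The window table and the commitment to use all available scores cannot both be followed.

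Take a subject who leaves Part B with a termination visit on Day 250. SVC, Norris, NfL and ALSAQ-40 from that visit map to Day 253, because Tables 2 and 3 cover Days 232–274. The ALSFRS-R from the same visit maps to nothing.

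The subjects concerned missed Day 253 or left the study around it. Section 4.7 assumes ALSFRS-R outcomes are missing at random. That assumption is easier to defend when the last score before dropout is in the model. If the gap is noticed only at programming, a rule must be invented then. Section 1.4 has the sponsor's biostatistics staff unblinded after the Part A lock, so that choice could be made with allocation known.

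**Working it through.** The check compares the Table 1 bounds with the scheduled visits, day by day.

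**1. The table's own rule.** Test lower = target − 14 and upper = target + 13:
- Day 225: 225 − 14 = 211; 225 + 13 = 238. Matches.
- Day 365: 365 − 14 = 351; 365 + 13 = 378. Matches.
- Day 1121: 1121 − 14 = 1107; 1121 + 13 = 1134. Matches.

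The rule reproduces all 18 rows.

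**2. Scheduled visits against rows.** The scheduled treatment-period ALSFRS-R visits are Days 29, 57, 85, 113, 141, 169, 197, 225, 253, 365, 449, 533, 617, 701, 785, 869, 953, 1037 and 1121, which is 19 visits. Table 1 has 18 rows. The visit without a row is Day 253, which is Week (253 − 1)/7 = 36.

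**3. The missing window.** Under the rule: 253 − 14 = 239 and 253 + 13 = 266. That is 266 − 239 + 1 = 28 days. It starts the day after the Day 225 window ends, so it creates no overlap.

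**4. What the row does and does not cover.** The interval now outside any window is Days 239–350, or 350 − 239 + 1 = 112 days. It divides as follows:
- Days 239–266, 28 days: due to the missing row.
- Days 267–350, 84 days: due to fixed 28-day windows, with no ALSFRS-R scheduled between Days 253 and 365.

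**5. The same design elsewhere.** Part C visits are 84 days apart and the windows are 28 days wide, so each interval leaves 84 − 28 = 56 days uncovered. There are nine such gaps, from 379–434 to 1051–1106. Uncovered days between Day 15 and Day 1134 are therefore 112 + 9 × 56 = 616 now, and 84 + 9 × 56 = 588 with the row added. The difference is the 28 days of step 3.

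**6. Analyses not touched.** The Part A windows run without a break from Day 15 to Day 182, so the primary endpoint is unaffected. By-visit summaries leave out unscheduled measurements under Section 3.2.5, so the missing row bears mainly on the MMRM.

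**The case against.** The strongest objection concerns size. A reader might infer that the missing row causes the loss of everything between Days 239 and 350. It does not. Step 4 shows that 84 of those 112 days would stay outside any window with the row restored. Tables 2 and 3 include Day 253 and still leave Days 275–343 unmapped. Windows with gaps between them are the section's general design, and narrow windows are defensible when function is declining. Stretching the Day 365 window backwards to close the gap would label scores taken weeks earlier as Week 52. That is a debatable trade-off and is not needed to correct an omission.

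A reader might also infer that the SAP orders these scores to be thrown away. It contains no such rule. It is silent on scores outside every window while promising to use all that are available. Exclusion is a fair inference from the categorical nominal-week model, but the documents support no more than an inconsistency.

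Nor do subjects who stop in Part B lose their last score in general. Termination scores on Days 183–238, or from Day 351 to Day 378, do map. The protocol also asks sites to attempt contact after termination and "conduct the ALSFRS-R assessment approximately every 28 days for the remaining duration of the study", but Section 4.9 does not say whether its windows apply to those assessments. They depend on consent and have no fixed days. If the windows do apply, the missing row affects only contacts falling in Days 239–266.

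These points limit the finding but do not remove it. No reason is given for leaving out Day 253, and the other two tables in the section include it.

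**Conclusion.** The omission is real, looks like an oversight, and is minor. Early-termination, unscheduled or make-up ALSFRS-R scores from Days 239–266 have no nominal visit and so cannot enter the nominal-week MMRM as written, contrary to the data rule in Section 5.2.1. Scores from the scheduled Day 253 visit keep their visit.

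The affected analyses are the extension comparisons at Weeks 52 and 160, for which Section 4.6 plans no multiplicity control. The conclusion rests on two readings of the SAP: that Table 1 is the only route by which such scores get a visit, and that the model uses nominal week only. The documents do not allow the number of affected scores, or any shift in the estimates, to be worked out.

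**What to change.** Add one row to Table 1 in Section 4.9 of the Parts B/C SAP: Day 253, lower bound 239, target 253, upper bound 266. This follows the rule behind every other row, overlaps nothing and changes no other window.

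Separately, the SAP could add a sentence on how ALSFRS-R scores outside every window are handled in the MMRM. That would cover Days 267–350 and the nine Part C gaps, and should say whether the windows apply to the assessments attempted after early termination.

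The cost is one table row, plus one sentence if the second step is taken. No data collection changes.
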